8. EXTENT OF EXPOSURE AND TREATMENT COMPLIANCE

8.1. Exposure to Investigational Product

The Active Treatment Period will be comprised of Open Label Treatment Period 1 and Open Label Treatment Period 2. During the Open Label Treatment Period 1, 75 mg or 225 mg subcutaneous (SC), will be administered at baseline and then every 4 weeks through Week 72 (Visit 19). Once the Open Label Treatment Period 1 has been completed, subjects may continue for Open Label Treatment Period 2 and will be assigned to the 75 mg dose.

- Exposure to the investigational product for the safety analysis set will be summarized in terms of treatment duration, which is calculated as the number of days from the date of first dose of investigational product taken in A7281010 to the date of the last dose investigational product taken in A7281010, inclusively. In addition, the number of injections of investigational product will be summarized both continuously and categorically (6, 12, 18, 24, 30, 36 injections received). Number of injections received for 75mg and 225 mg doses respectively will be presented as well. Descriptive statistics will be presented by treatment group defined in [Section 5](#).

8.2. Measurement of Treatment Compliance

Investigational product dosing compliance for a specified period is defined as the total number of injections actually administered during that period divided by the number of injections planned to be administered during the same period multiplied by 100. Compliance will be summarized by treatment group/Open Label Treatment Period.

Compliance during the treatment period 1 and 2 and overall will be calculated for each subject using the formula:

$$\text{Compliance} = (\# \text{ injections actually administered} / \# \text{ injections planned}) * 100$$

The definition of number of injections planned will be the injection schedule following the protocol (baseline to week 72, every 4 weeks for Open Label Treatment Period 1, week 76 to week 144, every 4 weeks for Open Label Treatment Period 2 and baseline to week 144, every 4 weeks for the overall compliance). For early withdrawal, it will be all the scheduled injections before the withdrawn dates.

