2. STUDY DESIGN

2.1. General Study Design

This is a multi-center Phase 2, open-label, safety extension study for the A7281009 study, which evaluated SHP647 in subjects with moderate to severe ulcerative colitis. Subjects eligible for this study will have completed the 12-week double-blind induction period in study A7281009 and must have discontinued immunosuppressant therapy. They will then enter into the Active Treatment period which consists of two consecutive 18 month periods. The first active period is called Open Label Treatment Period 1 (Weeks 0-72). All subjects will be randomly assigned to receive either 75 mg or 225 mg subcutaneously every 4 weeks without unblinding treatment assignment from the A7281009 study, and without regard to responder status in that study.

After completion of Open Label Treatment Period 1, all subjects will be permitted to continue in Open Label Treatment Period 2 (Weeks 76-144) and will receive the 75 mg dose every four weeks for a further 18 months.

After the active treatment period, the subjects will enter a 6 month follow up period including 2 visits 3 months apart. At the last onsite visit (Week 168), subjects will undergo an End of Study visit.

Eligible subjects will be asked if they would like to continue participation in an optional endoscopic substudy that will characterize the effect of SHP647 on mucosal healing and tissue biology. Participation in this part of the study will not affect participation in the main study. Approximately 40 subjects are needed for meaningful data. Data may be combined with the data from the other MAdCAM IBD studies. Details of the substudy analysis will not be included in this SAP and will be captured in an independent SAP.

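### SAP Section 8.2 does not limit planned injections to the periods entered or to time on treatment, so a subject who missed no dose can score from 51% to 100% on overall compliance.

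*SAP*

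**What the plan says.** Section 8.2 defines compliance for a period as the "total number of injections actually administered during that period divided by the number of injections planned to be administered during the same period", times 100. It is to be computed for each subject in Period 1, in Period 2 and overall.

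Planned injections follow the protocol schedule:
- Period 1: "baseline to week 72, every 4 weeks for Open Label Treatment Period 1"
- Period 2: "week 76 to week 144, every 4 weeks for Open Label Treatment Period 2"
- Overall: "baseline to week 144, every 4 weeks for the overall compliance"

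There is one exception: "For early withdrawal, it will be all the scheduled injections before the withdrawn dates".

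Elsewhere the SAP makes the second period optional. Section 2.1 says that "all subjects will be permitted to continue in Open Label Treatment Period 2", and Section 8.1 says "Once the Open Label Treatment Period 1 has been completed, subjects may continue for Open Label Treatment Period 2". The Period 2 schedule in Section 2.4 has a separate amendment consent at Week 76. Section 19.1.1 places the two follow-up visits 12 and 24 weeks after the last dose, whenever that dose was given.

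**The concern.** Completing Period 1 and stopping there is a permitted path, but Section 8.2 has no rule for it. The Period 2 and overall denominators are not restricted to subjects who entered Period 2. The early-withdrawal exception does not say whether such a subject counts as withdrawn, or whether the date is the end of treatment or the end of study participation. Because follow-up is timed from the last dose, those two dates can be about 24 weeks apart.

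A compliance figure should fall only when a dose that was due is not given. Under this rule it can also fall because a subject declined an optional period, or because follow-up time is counted as dosing time. Without a clearer rule, whoever programs the derivation has to choose the denominator.

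**Working it through.** The SAP gives no compliance percentage and no count of planned injections, so there is no stated figure to reproduce. The counts below come from the four-weekly schedule in Section 8.2.

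**Planned injections**
- Period 1, Weeks 0 to 72: 72/4 + 1 = 19
- Period 2, Weeks 76 to 144: (144 − 76)/4 + 1 = 18
- Overall, Weeks 0 to 144: 144/4 + 1 = 37 = 19 + 18

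**Case A: all 19 Period 1 doses received, Period 2 not entered.** Section 19.1.1 puts the end of follow-up at Week 72 + 24 = Week 96.

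| Reading of Section 8.2 | Planned overall | Overall compliance | Period 2 compliance |
|---|---|---|---|
| Not an early withdrawal | 37 | 19/37 = 51.4% | 0/18 = 0% |
| Withdrawn at Week 96 (end of follow-up) | Weeks 0 to 92 = 24 | 19/24 = 79.2% | 0/5 = 0% |
| Withdrawn at Week 84 (first follow-up visit) | Weeks 0 to 80 = 21 | 19/21 = 90.5% | 0/2 = 0% |
| Withdrawn after the Week 72 dose and by Week 76 | Weeks 0 to 72 = 19 | 19/19 = 100% | 0/0, undefined |

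Period 1 compliance is 19/19 = 100% in every row.

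**Case B: treatment stopped after the Week 40 dose, follow-up completed.** Doses given at Weeks 0 to 40: 40/4 + 1 = 11. End of follow-up: Week 40 + 24 = Week 64. Injections scheduled before Week 64 (Weeks 0 to 60): 60/4 + 1 = 16.
- Withdrawal means leaving the study: 11/16 = 68.75%, with no dose missed on treatment. Week 64 lies within Period 1, so this is also the Period 1 figure.
- Withdrawal means stopping the drug, dated after the Week 40 dose and by Week 44: 11/11 = 100%.

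**Effect on a group mean.** The SAP does not give the fraction p of subjects who complete Period 1 and do not enter Period 2. Assume everyone is otherwise perfectly adherent and all others receive 37 of 37. Mean overall compliance is then 100 − (100 − c)p, where c is the Case A result.

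| p (assumed) | c = 51.4% | c = 79.2% | c = 100% |
|---|---|---|---|
| 0.1 | 95.1% | 97.9% | 100% |
| 0.2 | 90.3% | 95.8% | 100% |
| 0.4 | 80.5% | 91.7% | 100% |

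**Boundary.** The exception counts injections scheduled strictly before the withdrawal date. If that date is the day of the Week 72 dose, 18 injections are planned and 19 given: 19/18 = 105.6%.

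**The case against.** A reader might infer that the plan will certainly report the Case A subject as 51% compliant. The text does not support that. The 51% requires that the subject is not an early withdrawal, and no section says so. Footnote j to the Period 2 schedule in Section 2.4 names two ways out of the study, the early withdrawal visit or completion at Week 168. Someone finishing follow-up at Week 96 fits the first better, which gives 79% to 100%.

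The 69% in Case B is also one reading. Section 11.1 uses withdrawal for stopping the investigational product too, and on that usage Case B scores 100%. Footnote j, however, uses early withdrawal for leaving the study, and Section 8.2 adopts neither sense explicitly. The 51% and the 69% also rest on different classifications, so they should not be presented as the joint result of one rule.

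A reader might further infer that compliance is the plan's only view of how much drug was delivered, or that the comparison between the two assigned doses is distorted. Neither follows. Section 8.1 also summarises treatment duration and number of injections, in total and by dose, and Section 5 tabulates entry into and discontinuation from each period. The two doses are assigned only in Period 1, where the Period 1 completer scores 100% on every reading in the Case A table. Subjects who stop within Period 1, as in Case B, can still be affected there.

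Nothing is tested (Sections 2.5 and 2.6), and no analysis set in Section 4 uses a compliance threshold. The protocol may define early withdrawal; it was not available for this check. Such a definition could settle which row of the Case A table applies. It would not by itself limit the Section 8.2 denominator to periods entered or to time on treatment.

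**Conclusion.** The point holds as a minor one. As written, Section 8.2 allows overall compliance of 51%, 79%, 90% or 100% for the same fully adherent Period 1 completer, and 0% or an undefined value in Period 2. If withdrawal means leaving the study, as in footnote j, injections count as planned after treatment has ended, and a Week 40 stopper with no missed dose scores 69%.

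These results rest on the four-weekly schedule, the optional status of Period 2, and follow-up timed from the last dose, all stated in the SAP. The effect on group means depends on p, which is not given, and on which reading is programmed. The damage is limited to the interpretation of a descriptive summary: mainly the overall and Period 2 figures, and the Period 1 figure for subjects who stop within that period.

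**What to change.** In Section 8.2:
- Count planned injections only in periods that the subject entered. Within each, count up to and including the date of treatment discontinuation, or to the end of the period if completed.
- Take the overall denominator as the sum over periods entered.
- Compute Period 2 compliance only in subjects who entered Period 2, and show their number.
- Replace the reference to withdrawn dates with the date of treatment discontinuation. State that this is the date of the decision to stop, so that doses missed before that decision still count as planned.

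Under this rule Case A gives 19/19 = 100% overall with no Period 2 value, and Case B gives 11/11 = 100% if the decision is made before the Week 44 dose is due. Missed doses still lower the figure.

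The cost is a few lines of SAP text and one derivation. Period entry and treatment discontinuation are already needed for the disposition table in Section 5; the only addition is to confirm that the discontinuation date is recorded. No other analysis changes.

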9. PRIOR AND CONCOMITANT MEDICATION

Version dated 01 December 2016 of the WHO Drug Dictionary will be used to classify prior and concomitant medications by preferred term name.

Prior medication is defined as any medication with the start date prior to the date of the first dose of investigational product within A7281010.

Concomitant medication is defined as any medication with a start date prior to the date of the first dose of investigational product and continuing after the first dose of investigational product or with a start date between the dates of the first and last doses of investigational product, inclusive. Any medication with a start date after the date of the last dose of investigational product will not be considered a concomitant medication.

All the medications from A7281009 study will be imported to A7281010 study. If the medication is discontinued at end of study A7281009, it will be considered as Prior for study A7281010 whereas if medication is ongoing, then it will be considered as concomitant for study A7281010

Both prior and concomitant medication usage will be summarized by the number and percentage of subjects in each treatment group receiving each medication within each preferred term for the safety analysis set. Medications can be counted both as prior and concomitant medication. Multiple medication usage by a subject in the same category will be counted only once.

All prior and concomitant medication will be listed.

Subjects in the follow up period will be characterized by additional biologic therapy (anti-TNF (Adalimumab, Certolizumab, Certolizumab Pegol, Golimumab, Infliximab), Vedolizumab and Other Biologics (Ustekinumab)) and summarized by treatment group. Additional biological therapies will be listed.

10. EFFICACY ANALYSES

The safety analysis set will be used for all efficacy analyses. No formal statistical analyses will be performed. Descriptive statistics will be provided for the exploratory efficacy analysis. The continuous variables will be summarized with n, mean, standard deviation, minimum, median and maximum by treatment and time point. The categorical endpoints will be summarized with frequency counts and percentages by treatment and time point. All summaries will be presented by A7281010 treatment group as defined in [Section 5](#).

10.1. Primary Efficacy Endpoint(s) and Analysis

Not applicable

10.2. Secondary Efficacy Endpoint(s) and Analysis

The proportion of subjects with mucosal healing (defined as absolute Mayo subscore for endoscopy of 0 or 1), along with their corresponding 90% confidence intervals based on the Wilson score method, at Baseline and Week 16 will be listed and summarized by the treatment groups as defined in [Section 5](#) and their treatment in the A7281009 study (Placebo vs. SHP647) and overall. These three tables will be presented based on centrally read Mayo subscores only. This will initially be based on the non-responder imputation method (please see [Section 17.2.1](#)). These summaries will be produced for all subjects, for subjects who were deemed to be clinical responders in A7281009 and for non-responders in A7281009.

These three tables will be repeated based on the observed cases rather than the non-responder imputation method.

Bar graphs with confidence intervals will also be presented for these summaries.

10.3. Exploratory Efficacy Endpoint(s) and Analyses

10.3.1 Total Mayo, Partial Mayo, SCCAI Clinical Response and Clinical Remission

The proportion of subjects with Clinical Response at Baseline and at Week 16 (based on Total Mayo score and defined in Table 2, below and using the A7281009 baseline) will be presented in the same way as mucosal healing (defined in [Section 10.2](#)).

The proportion of subjects with Clinical Remission at Baseline and at Week 16 (based on Total Mayo score and defined in Table 2, below) will be presented in the same way as mucosal healing (defined in Section 10.2). In addition, the proportion of patients with Clinical Remission at Baseline and Week 16 will also be presented by remission status in A7281009 and imputation method.

The proportion of subjects with Clinical Response based upon the partial Mayo Score (using the A7281009 baseline) along with the corresponding 90% Wilson confidence intervals will be summarized by the treatment groups defined in Section 5 and their treatment in the

A7281009 study (Placebo vs. SHP647) and overall by monthly visits. This summary table will be produced for both the non-responder imputation method and the observed case.

The proportion of subjects with Clinical Remission based upon the partial Mayo Score will be presented in the same way as the Clinical Response based on the partial Mayo score.

The proportion of subjects with Clinical Response based upon SCCAI (using the A7281009 baseline) along with the corresponding 90% Wilson confidence intervals will be summarized by the treatment groups defined in [Section 5](#) and their treatment in the A7281009 study (Placebo vs. SHP647) and overall by monthly visits. This summary table will be produced for both the non-responder imputation method and the observed case.

The proportion of subjects with Clinical Remission based upon the SCCAI will be presented in the same way as the Clinical Response based on the SCCAI.

Definitions of remission, response and relapse for the Total Mayo, Partial Mayo, and SCCAI are given in Table 2, Table 3 and Table 4.

In addition, the Total Mayo Score, Partial Mayo Score, individual Mayo Subscores, and SCCAI data at baseline from both A7281009 and A7281010 study and the change from baseline of A7281009 over time will be presented by their treatment groups in study A7281010 and A7281009 and overall. Total Mayo Score and endoscopic subscore will be summarized by source of sigmoidoscopy (Centrally or locally read) separately. In addition, categorical summary will also be provided for the subscores in Mayo scores.

Table 2: Total Mayo Score	
Clinical Remission	Total Mayo Score of 2 points or lower with no individual subscore exceeding 1 point and rectal bleed subscore of 0 or 1.
Clinical Response	A decrease from baseline of at least 3 points in total Mayo score with at least a 30% change, accompanied by at least one point decrease or absolute score of 0 or 1 in rectal bleeding subscore

Table 3: Partial Mayo Score	
Clinical Remission	Partial Mayo Score of 2 points or lower with no individual subscore exceeding 1 point and rectal bleed subscore of 0 or 1.
Clinical Response	A decrease from baseline of at least 2 points in partial Mayo score with at least a 30% change, accompanied by at least one point decrease or absolute score of 0 or 1 in rectal bleeding subscore

Table 4: Simple Clinical Colitis Activity Index

Clinical Remission	Total SCCAI score of <2 points
Clinical Response	Decrease in SCCAI score of ≥ 3 points

10.3.2 Dose Escalation

For the table for dose escalation only subjects with starting dose of 75mg will be included. Time to dose escalation in subjects for loss of response will be summarized using Kaplan estimates at 0-8, >8-12, >12-16 in 4 week intervals up to >72, together with their SE will be provided. The number and percentage of subjects who experienced dose escalation and censored (subjects who discontinued during the time period or don't have further dosing data after the time period) at each 4 week interval will be presented. The associated Kaplan-Meier plot will be produced.

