5. SUBJECT DISPOSITION

The number of subjects included in each subject set will be summarized by the following treatment groups:

- SH647 75mg no escalation - this comprises all data for patients who receive 75mg throughout the Open Label Treatment Period 1.
- SHP647 75->225 mg – this comprises all data for patients who (prior to protocol amendment 3) up-titrated from 75 mg to 225 mg in Open Label Treatment Period 1.
- SHP647 75 mg overall – this comprises all patients who were randomized to 75 mg in Open Label Treatment Period 1.
- SHP647 225mg – this comprises all patients who were randomized to 225 mg in Open Label Treatment Period 1.
- SHP647 all doses – this comprises all patients.

A subject disposition table will be provided. The subject disposition table will include the number and percentage of subjects included in each subject set. It will also include number and percentage of subjects enrolled, randomized, treated, entering Open Label Treatment Period 1, Open Label Treatment Period 2, follow up period, discontinuing from the study, discontinuing from Open Label Treatment Period 1, Open Label Treatment Period 2, follow up period and discontinuing from the treatment. A detailed summary of the primary reasons for discontinuation from the study and discontinuation from treatment will be presented by treatment group. The percentages will use the number of subjects in the safety analysis set as the denominator and will be presented by the treatment groups defined above. The subject disposition table will be based on the enrolled set.

All subjects who prematurely discontinued during the study will be listed.

The number of subjects enrolled, randomized and completed will be tabulated by site and country. In addition, the duration of enrollment, in days, will be summarized for each site, country, and overall. Duration of enrollment will be calculated as (last date of contact for any subject at that site - the first date of screening or enrollment for any subject at that site + 1).

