14. INTERIM ANALYSIS

14.1. Interim Analyses

Two interim analyses (IAs) were planned to be performed for this study when 50% of subjects from the Phase 2 study (A7281009) had been enrolled in this study (A7281010), and the last subject from the Phase 2 study (A7281009) had been enrolled in this study (A7281010). In practice, two IAs occurred, one at the time of the topline report for the A7281009 study and one for an end of phase 2 meeting. The purpose of the IAs was to provide additional data on the durability of response, remission, and safety from A7281009, to facilitate the decision-making process of future studies.

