16. CHANGES TO ANALYSES SPECIFIED IN PROTOCOL

Dose escalation was removed in protocol amendment 3, SAP accommodates for subjects enrolled under prior to protocol amendment.

Gene expression profiling (mRNA) and proteins will not be analyzed. JC Virus DNA will not be analyzed.

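### The Kaplan-Meier analysis of dose escalation censors treatment discontinuation and ignores the removal of escalation in protocol amendment 3, so the curve does not estimate the proportion of 75 mg starters escalated

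*SAP*

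**What the plan says.** SAP Section 10.3.2 sets the population: "For the table for dose escalation only subjects with starting dose of 75mg will be included". It sets the estimator: "Time to dose escalation in subjects for loss of response will be summarized using Kaplan estimates at 0-8, >8-12, >12-16 in 4 week intervals up". The intervals run past Week 72, and standard errors are given. A curve is added: "The associated Kaplan-Meier plot will be produced". The same table gives, per interval, "The number and percentage of subjects who experienced dose escalation and censored", where censoring covers "censored (subjects who discontinued during the time period or don't have further dosing data after the time period". Discontinuation is therefore pooled with the end of dosing data. No competing event, cumulative incidence function or sensitivity analysis is specified.

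Two other sections bear on this. Section 5 says "A detailed summary of the primary reasons for discontinuation from the study and discontinuation from treatment will be presented by treatment group", but does not link those reasons to the escalation analysis. It also limits the 75 to 225 mg group to subjects up-titrated before amendment 3. Section 16 states "Dose escalation was removed in protocol amendment 3, SAP accommodates for subjects enrolled under prior to protocol amendment". The censoring rule in Section 10.3.2 does not take this into account.

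**The concern.** Kaplan-Meier censoring assumes that a censored subject could still have the event later, at the same rate as those who remain under observation. A subject who has stopped the drug cannot be moved to the higher dose. Censoring that subject assigns the later escalation risk of those still dosing to someone whose risk is zero. One minus Kaplan-Meier then describes a hypothetical setting in which nobody stops. It lies above the proportion who were in fact escalated, whatever the reasons for stopping.

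The opposite problem arises after amendment 3. A subject who continues on 75 mg without the option to escalate is neither an event nor censored under the rule. That subject adds to the number at risk without being at risk, which lowers the estimate relative to the probability among those who could escalate.

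What is at stake is the meaning of one planned table, its standard errors and its figure. A reader will take the curve as the share of 75 mg starters escalated by a given week, and it is not that.

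**Working it through.** The SAP gives no escalation or discontinuation rate, so there is no planned figure to reproduce. All rates below are assumptions; only the 72-week horizon and the intervals come from the SAP.

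**1. Constant weekly hazards over 72 weeks.** Let a be the escalation hazard and d the discontinuation hazard.

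- Planned quantity: 1 − KM = 1 − exp(−72a).
- Proportion actually escalated: CIF = a/(a + d) × [1 − exp(−72(a + d))].

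For a = 0.004, 1 − KM = 1 − exp(−0.288) = 25.0%. For a = 0.006, 1 − KM = 1 − exp(−0.432) = 35.1%.

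| a | d | 1 − KM | CIF | Excess (points) |
|---|---|---|---|---|
| 0.004 | 0.002 | 25.0% | 23.4% | 1.6 |
| 0.004 | 0.004 | 25.0% | 21.9% | 3.1 |
| 0.004 | 0.008 | 25.0% | 19.3% | 5.7 |
| 0.006 | 0.002 | 35.1% | 32.8% | 2.3 |
| 0.006 | 0.004 | 35.1% | 30.8% | 4.3 |
| 0.006 | 0.008 | 35.1% | 27.2% | 7.9 |

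If stopping were the only exit, the three values of d would mean 13%, 25% and 44% stopped by Week 72, from 1 − exp(−72d).

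**2. The same comparison in observed proportions.** Let E be the proportion escalated and D the proportion stopped before escalation. Under proportional constant hazards, 1 − KM = 1 − (1 − E − D)^(E/(E + D)).

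- E = D = 10%: 10.6% against 10.0%.
- E = D = 20%: 22.5% against 20.0%.
- E = D = 30%: 36.8% against 30.0%.
- E = D = 40%: 55.3% against 40.0%.

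For E and D each between 10% and 40%, the excess runs from 0.6 to 15.3 points and is never negative.

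**3. On the SAP's own intervals.** About 270 subjects (Section 2.5) allocated 1:1 (Section 2.2) gives about 135 starting on 75 mg. With 27 escalated and 27 stopped, one minus Kaplan-Meier is 22.4% against 20.0%. With 40 and 40 it is 35.8% against 29.6%.

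**4. Effect of amendment 3.** Suppose that among subjects able to escalate, E = 30% and D = 20%. Suppose also that a share g of 75 mg starters can never escalate, stops at the same discontinuation hazard and stays in the risk set. With g = 0, 1 − KM = 1 − 0.5^0.6 = 34.0%. In general 1 − KM = (1 − g) × 34.0%, and the proportion escalated among all starters is (1 − g) × 30%.

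| g | 1 − KM | Escalated, all starters | Escalated, those able to |
|---|---|---|---|
| 0% | 34.0% | 30.0% | 30.0% |
| 25% | 25.5% | 22.5% | 30.0% |
| 50% | 17.0% | 15.0% | 30.0% |

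The planned curve is too high against all 75 mg starters and, with g at 25% or 50%, too low against those who could escalate. Changing the estimator alone would give 22.5% or 15.0%, further from 30%. Restricting to subjects able to escalate and using the cumulative incidence gives 30%.

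**The case against.** The strongest reply is that the crude proportion is already planned. The table reports escalations per interval, and Section 5 counts both the escalated group and all subjects randomized to 75 mg. If stopping were the only exit before Week 72, the Aalen-Johansen estimate would equal that crude proportion. This stands in part and lowers the impact. It does not rescue the curve or its standard errors, which still attach to a different quantity. Nor can a reader separate stopping from other censoring in the table, because the two are pooled.

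Materiality is also fairly questioned. The efficacy summaries are descriptive (Section 10), and Section 2.5 states that there are no hypotheses or decision rules. With about 135 starters, the standard error of a 25% estimate is roughly √(0.25 × 0.75/135) = 3.7 points, and the middle excess for that estimate, 3.1 points, is smaller. This stands as a limit on importance. The excess is nevertheless systematic and avoidable.

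A reader might go further and infer that the curve under-counts loss of response on 75 mg, because a subject who leaves for lack of efficacy is censored. The SAP does not support this as a finding:

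- The endpoint is escalation. Section 10.3.2 names loss of response as the reason for escalating and does not offer the curve as a measure of it.
- Response over time is handled in Section 10.3.1, by monthly partial Mayo and SCCAI summaries. Section 17.2.1 counts drop-outs there as non-responders.
- The net direction depends on the share of discontinuations due to loss of response, which the SAP does not give. With E = D = 20%, the curve falls below escalations plus such discontinuations only if that share exceeds (22.54 − 20)/20, about 13%. With E = D = 40% the threshold is (55.28 − 40)/40, about 38%.

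**Conclusion.** The concern holds for the escalation estimate. Section 10.3.2 treats an event that precludes escalation as ordinary censoring, so one minus Kaplan-Meier overstates the proportion of 75 mg starters actually escalated. The direction follows whenever subjects stop and others escalate afterwards. The size, about 2 to 8 points, rests on the assumed constant weekly hazards (0.004 to 0.006 and 0.002 to 0.008).

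The rule also leaves subjects in the risk set after amendment 3 removed the option to escalate. How much this matters depends on how many subjects were affected and when, which the SAP does not say. For that reason an unqualified statement that the curve is too high would also go too far: it is too high against all 75 mg starters, but can be too low against those able to escalate.

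The impact is minor. The table is exploratory, and the crude proportion can be partly recovered from other planned output. The correction is still worth making because it costs little.

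**What to change.** Amend Section 10.3.2 as follows:

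1. Estimate escalation by the Aalen-Johansen cumulative incidence function, with treatment discontinuation before escalation as a competing event, at the same intervals and with standard errors. Replace the Kaplan-Meier plot with this curve, or show it alongside.
2. Restrict or censor follow-up at the time each subject came under protocol amendment 3, and state which date defines this. Make this change together with the first, since the new estimator alone does not deal with it.
3. In the interval counts, show discontinuation separately from other censoring.
4. Optionally, if the recorded discontinuation reasons allow it, add a supplementary display of the composite of escalation or discontinuation for lack of efficacy. Section 5 promises primary reasons but lists no categories, so check this first.

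The cost is a few lines of SAP wording, a standard option in the planned SAS software, the amendment 3 date for each subject, and one replaced or extra curve. Treating discontinuation as competing gives a somewhat lower escalation figure; handling amendment 3 may raise it.
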